### **1.3.7 Long term Follow-up phase**

Subjects will remain in the follow-up phase of the trial for up to 3 years until start of another therapy, withdrawal of consent, or death. Subjects or their caretakers will be contacted by a member of the study team every 12 weeks ( $\pm$  28 days) to collect post-study survival status (alive or deceased) and receipt of subsequent anticancer therapy (yes or no). If available, start date and type of subsequent anticancer therapy should be documented in the medical record or research shadow chart. Any method of data collection is acceptable for long-term follow-up (medical records, phone, electronic means, social security death index website, etc.) The source of the information should be noted in the medical record or research shadow chart.

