### Pembrolizumab and Nivolumab Dose Modifications

No dose reductions of pembrolizumab or nivolumab are allowed. PD-1 inhibitor must be withheld (not delayed) for drug-related toxicities

Adverse events (both non-serious and serious) associated with PD-1 inhibitor exposure may represent an immunologic etiology. These adverse events may occur shortly after the first dose or several months after the last dose of treatment. For suspected immune-mediated adverse reactions, ensure adequate evaluation to confirm etiology or exclude other causes.

**Grade 3-4 toxicity.** For Grade 3-4 immune-related adverse event (irAE) related to PD-1 inhibitor, withhold PD-1 inhibitor and if indicated, administer corticosteroids as per immune related adverse event guidelines. Upon improvement to Grade 1 or less, initiate corticosteroid taper and continue to taper over at least 4 weeks. Resume PD-1 inhibitor when the adverse reaction remains at Grade 1 or less following corticosteroid taper.

Permanently discontinue PD-1 inhibitor for any Grade 3 immune-mediated adverse reaction that recurs and for any life-threatening immune-mediated adverse reaction. If steroids are indicated longer than 8 weeks, the subject must discontinue treatment with PD-1 inhibitor.

Upon improvement to Grade 1 or less, the subject may resume treatment. The PD-1 inhibitor dose should be skipped (not delayed) and treatment should resume at the next scheduled timepoint.

If the toxicity is liver-related, trigriluzole must also be held (see above). Otherwise, PD-1 inhibitor therapy may be continued at the discretion of the treating investigator.

**Grade 3-4 toxicity.** For Grade 3-4 toxicity that is treatment-emergent and but not an irAE, (examples: fatigue, nausea), PD-1 inhibitor will be held until improvement of toxicity to a Grade 0-1.

**Grade 1-2 Toxicity.** Grade 1-2 adverse events do not require dose adjustment, except if the patient/physician considers them to be serious or intolerable—in this case, the PD-1 inhibitor may be held at the discretion of the treating investigator. An example is grade 2 fatigue.

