**RUTGERS | eIRB**  
**APPROVED**

IRB ID: Pro20170000453  
Approval Date: 10/4/2019  
Expiration Date: 4/3/2020

Footnotes

1. Screening evaluations must be performed no more than 28 days prior to registration. The subject must begin study treatment no more than 14 days after registration.
2. Routine safety labs: CBC with Differential, Comprehensive Metabolic Panel, Amylase, Lipase, TSH, Free T4, LDH. Routine safety labs do not need to be repeated on Week -2 if performed in the past 14 days. More frequent labs may be performed as clinically necessary, as determined by treating investigator. WOCBP must have a negative serum beta-HCG pregnancy test prior to the first dose. During study treatment, pregnancy testing may be performed as indicated at the treating physician's discretion.
3. ECG monitoring is to be performed at the following treatment visits: a) at baseline (prior to dose on start date Week -2), and at expected  $C_{max}$  4 hours post trigriluzole (window  $\pm$  30 minutes), b) at steady state on Week -1 and c) at steady state at Week 1 (untimed), d) at steady state at weeks 7, 13, 25, 37, and 49. If trigriluzole has been discontinued, EKG monitoring may be discontinued.
4. Research blood collection for PK analysis is to be performed at the following treatment visits: a) start date (Week -2) at pre-treatment, and at 2 hours and 4 hours post trigriluzole (window  $\pm$  30 minutes), b) Week 1 (untimed sample, pre-infusion), and c) Week 7 (untimed sample, pre-infusion). No PK collections after Week 7.
5. Research blood collection for correlative studies is to be performed at Screening/Week -2 (pre-treatment, untimed), Week 1 (pre-infusion, untimed), Week 7 (pre-infusion, untimed), and Week 13 (pre-infusion, untimed). Baseline research blood and tumor samples may be performed anytime prior to the start of therapy. Ideally, the research blood samples should be collected 3-14 days prior to the fresh tumor biopsy, but it is also acceptable to collect them on the same day. No research bloods after Week 13.
6. Tumor Tissue Collection. Archival tissue (a block or 6-10 unstained slides) will be obtained for all subjects, when available. Research biopsies are optional but strongly encouraged at Baseline/Week -2, and Week 1, and Week 7. No biopsies after Week 7.
7. Tumor Assessment must be performed at Screening, Weeks 7, 13, 25, 37, 49, 61, 73, 85, 97, and 109.
8. Q4 weeks starting from Week 13: Weeks 13, 17, 21, 25, 29, 33, 37, 41, 45, 49, etc.

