**RUTGERS | eIRB**  
**APPROVED**

IRB ID: Pro20170000453  
Approval Date: 10/4/2019  
Expiration Date: 4/3/2020

Footnotes

1. Screening evaluations must be performed no more than 28 days prior to registration. The subject must begin study treatment no more than 14 days after registration.
2. Routine safety labs: CBC with Differential, Comprehensive Metabolic Panel, Amylase, Lipase, TSH, Free T4, LDH. Routine safety labs do not need to be repeated on Week -2 if performed in the past 14 days. More frequent labs may be performed as clinically necessary, as determined by treating investigator. WOCBP must have a negative serum beta-HCG pregnancy test prior to the first dose. During study treatment, pregnancy testing may be performed as indicated at the treating physician's discretion.
3. ECG monitoring is to be performed at the following treatment visits: a) at baseline (prior to dose on start date Week -2), and at expected Cmax 4 hours post trigriluzole (window  $\pm$  30 minutes), b) at steady state on Week -1 and c) at steady state at Week 1 (untimed), and d) at steady state at weeks 7, 13, 25, 37, and 49. If trigriluzole has been discontinued, EKG monitoring may be discontinued.
4. Research blood collection for PK analysis is to be performed at the following treatment visits: a) start date (Week -2) at pre-treatment, and at 2 hours and 4 hours post trigriluzole (window  $\pm$  30 minutes), b) Week 1 (untimed sample, pre-infusion), and c) Week 7 (untimed sample, pre-infusion). No PK collections after Week 7.
5. Research blood collection for correlative studies is to be performed at Screening/Week -2 (pre-treatment, untimed), Week 1 (pre-infusion, untimed), Week 7 (pre-infusion, untimed), and Week 13 (pre-infusion, untimed). Baseline research blood and tumor samples may be performed anytime prior to the start of therapy. Ideally, the research blood samples should be collected 3-14 days prior to the fresh tumor biopsy, but it is also acceptable to collect them on the same day. No research bloods after Week 13.
6. Tumor Tissue Collection. Archival tissue (a block or 6-10 unstained slides) will be obtained for all subjects, when available. Research biopsies are optional but strongly encouraged at Baseline/Week-2, Week 1, and Week 7. No biopsies after Week 7.
7. Tumor Assessment must be performed at Screening, Weeks 7, 13, 25, 37, 49, 61, 73, 85, 97, and 109.
8. Q6 weeks: Weeks 13, 19, 25, 31, 37, 43, and 49, etc.

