 **RUTGERS | eIRB**  
APPROVED  
Form Version v120116

IRB ID: Pro20170000453  
Approval Date: 10/4/2019  
Expiration Date: 4/3/2020

	Off treatment but on study Q6 weeks	Off treatment but on study Q12 weeks	Safety Follow-up (12 weeks after last dose of rx)	Long-Term Follow-up Q12 weeks
Scheduling Window (Days):	±14	±14	±28	± 28
Prior and Concomitant Medication Review	X	X	X	
Assess Baseline Symptoms/Adverse Events and Compliance	X	X	X	
Vital Signs and Weight, ECOG Performance Status, Physical Examination	X	X	X	
Routine Safety Laboratory Studies	X	X	X	
Tumor Assessment 		X	X	
Post-study survival status, and receipt of subsequent anticancer therapy				X

Footnotes

1. If a subject has discontinued active treatment due to reasons other than PD (such as toxicity or patient preference), the subject will continue to have CT scans and follow-up visits to monitor them until Week 49.
2. Tumor Assessment must be performed at the same Weeks as subjects who remain on active treatment (Week 7, Week 13, and then Q12 weeks up until Week 49).
3. Safety follow-up visit will occur at Week 61 for subjects who complete all treatment (Week 49), but it will occur prior to Week 61 if active treatment is discontinued early for PD or other reasons.
4. Long-term Follow-up. Subjects will remain in the follow up phase of the trial for up to 3 years until the start of another therapy, withdrawal of consent or death.

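### Footnote 3 of the follow-up calendar dates the safety visit from a Week 49 end of treatment, although treatment may run to Week 109 and the column header counts from the last dose

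*Combined protocol and SAP*

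**What the plan says.** Sections 1.3.2, 1.3.5 and 1.7.13 each allow treatment for up to 109 weeks, and both treatment calendars in Section 1.10 schedule dosing visits to Week 109.

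The follow-up calendar in Section 1.10 gives the safety visit two timings. The column header reads "Safety Follow-up (12 weeks after last dose of rx"), with a scheduling window of ±28 days. Footnote 3 to that header reads "Safety follow-up visit will occur at Week 61 for subjects who complete all treatment (Week 49), but it will occur prior to Week 61" when treatment is discontinued early for progression or another reason.

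Two other provisions govern what is collected after treatment. Under footnote 1 of the same calendar, a subject who stops for a reason other than progression is followed so that "the subject will continue to have CT scans and follow-up visits to monitor them until Week 49". Under Section 1.3.7, subjects in long-term follow-up are contacted every 12 weeks "to collect post-study survival status (alive or deceased) and receipt of subsequent anticancer therapy (yes or no").

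**The concern.** Footnote 3 equates finishing treatment with Week 49, which is not the end of treatment anywhere else in the treatment plan. It names no date later than Week 61 for any subject. For someone treated well past Week 49, it therefore places a post-treatment visit during treatment, while the header above it places the visit after treatment.

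The date matters because little else is scheduled for these subjects. The off-treatment visits end at Week 49 (footnote 1), or at one year from the start of treatment as Section 1.3.6 puts it. Long-term follow-up records only survival and later therapy. For a subject who stops after Week 49, the safety visit is thus the only scheduled post-treatment contact with examination, safety labs and adverse event review. On PD-1-related events, Section 1.7.7 itself says: "These adverse events may occur shortly after the first dose or several months after the last dose of treatment". In a trial whose primary objective is safety, the visit best placed to find such events should not carry two incompatible dates.

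**Working it through.** **Inputs**

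- Maximum treatment: Week 109 (Sections 1.3.2, 1.3.5 and 1.7.13; both treatment calendars).
- Header rule: last dose + 12 weeks, window ±28 days = ±4 weeks (follow-up calendar).
- Footnote 3: treatment complete at Week 49, visit at Week 61, earlier if treatment stops early.

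Let L be the week of the last dose. The header date is L + 12, with window L + 8 to L + 16.

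**Step 1. Reproduce the plan's figure.** With L = 49, 49 + 12 = 61. The footnote is the header rule applied to a Week 49 end. For earlier stops L + 12 is below 61, which also agrees with the footnote.

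**Step 2. Apply the header to full treatment.** With L = 109, 109 + 12 = 121. Week 61 is 109 − 61 = 48 weeks before treatment ends and 121 − 61 = 60 weeks before the header date.

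**Step 3. When is Week 61 inside the header's window?** It requires L + 8 ≤ 61 and L + 16 ≥ 61, so 45 ≤ L ≤ 53.

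**Step 4. Allow ±4 weeks around both dates.** The footnote's range becomes Weeks 57 to 65. Overlap with L + 8 to L + 16 at the upper end requires L + 8 ≤ 65, so L ≤ 57. After Week 57 no date meets both.

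**Step 5. Check the early-stop clause.** With L = 80, the header gives 80 + 12 = Week 92. The footnote, read literally, asks for a date before Week 61, which is more than 80 − 61 = 19 weeks before the last dose.

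| Last dose (week) | Header date (window) | Latest date under footnote 3 (with ±4 weeks) | Common date? |
|---|---|---|---|
| 49 | 61 (57–65) | 61 (65) | Yes |
| 53 | 65 (61–69) | 61 (65) | Yes |
| 57 | 69 (65–73) | 61 (65) | Week 65 only |
| 80 | 92 (88–96) | before 61 (65 at most) | None |
| 109 | 121 (117–125) | 61 (65) | None |

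**Step 6. Could the restart option explain it?** Section 1.3.6 lets a subject whose cancer returns or progresses restart for up to 12 more months with the PI's approval. That does not reconcile the dates. The three sections giving 109 weeks do not tie that figure to a restart, and the treatment calendars show continuous visits to Week 109.

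**The case against.** The best defence is that the header is a complete rule and the footnote only works it through for an older end date. Nobody would sensibly hold a post-treatment visit while the subject is still being dosed, so staff would probably follow the header. This stands, and it limits the practical harm: the 48-week gap is what the footnote says literally, not a forecast of conduct. It does not remove the contradiction, because the footnote is attached to that header and is the more specific text.

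A reader might infer more than the documents support, in three ways.

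- **Lost adverse event data.** Section 1.7.11 records adverse events to 30 days after the last dose, and SAE reporting runs for the same period or until later therapy starts, if sooner. Neither depends on footnote 3. The 12-week visit lies beyond those windows, so its date bears on clinical review of late events.
- **Different dating between sites.** Section 2.3 lists one research site and Section 3.0 marks multi-site coordination as not applicable. Other sections mention a satellite site and collaborating institutions, so the position is unclear. The plainer risk is inconsistency among staff.
- **A matching error in the ECG schedule.** Footnote 3 of both treatment calendars lists the later ECGs "at steady state at weeks 7, 13, 25, 37, and 49", whereas footnote 7 carries tumor assessment to Week 109: "Tumor Assessment must be performed at Screening, Weeks 7, 13, 25, 37, 49, 61, 73, 85, 97, and 109". The ECG list carries no explicit stop statement like those for PK, research blood and biopsies, which suggests a leftover. But the list is explicit, nothing requires an ECG after Week 49, the protocol reports no cardiac signal, and stopping after about a year of stable dosing is a possible choice. No ECG can be called missed.

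**Conclusion.** Footnote 3 is wrong as written. It conflicts with the 109-week treatment period and with its own column header. This is a minor internal inconsistency in an operational safety rule. The two timings agree for a Week 49 end, can both be met within the windows up to a last dose at Week 57, and cannot be met together after that. At full treatment they differ by 60 weeks.

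The Week 57 limit assumes that the column's ±28 days also applies to the footnote's Week 61; without that allowance the limit is Week 53. How many subjects would be treated past either week is not stated, so the number affected is unknown. No effect on the MTD/RP2D is shown. DLTs are assessed in the first weeks of treatment, far from the dates in question. The Week 49 end of the ECG list is a matter for clarification, not a finding of error.

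**What to change.** Replace footnote 3 of the follow-up calendar with: *Safety follow-up visit occurs 12 weeks (±28 days) after the actual last dose, whenever treatment ends (Week 121 after treatment to Week 109).*

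The cost is one footnote in an amendment. No visit or procedure is added, because the column header already plans this visit.

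As a query only, ask the sponsor whether the ECG list is meant to end at Week 49 and, if so, to say so in footnote 3 of both treatment calendars. If ECGs were meant to continue at 12-week spacing, Weeks 61, 73, 85, 97 and 109 would add at most five per subject, at visits already scheduled for tumor assessment. That is the sponsor's decision and not part of this correction.

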## **2.0 Project Management**

### **2.1 Research Staff and Qualifications**

The Phase I/Developmental research team (Investigators, nurses, data coordinators, regulatory specialists, etc) is part of the RCINJ Office for Human Research Subjects and Rutgers University. Annual compliance and human subjects training is required.

### **2.2 Resources Available**

N/A

### **2.3 Research Sites**

Rutgers Cancer Institute of New Jersey (RCINJ)

## **3.0 Multi-Site Research Communication & Coordination**

N/A

## **4.0 Research Data Source/s**

### **4.1 Primary Data-Subjects and Specimens**

#### **4.1.1 Subject Selection and Enrollment Considerations**

##### **Recruitment Details**

The subjects will be adults age 18 years and older who have a diagnosis of advanced cancer for whom medical therapy is indicated. Advanced cancer patients will be recruited specifically for this prospective study evaluating the safety of combining trigriluzole with PD-1 blocking antibody. After written informed consent is obtained, each subject will undergo screening for inclusion and exclusion criteria. These criteria, assessed by experienced clinical investigators who are familiar with expected toxicities of the drugs, help ensure the selection of the subjects who stand to benefit the most and the exclusion of medically inappropriate subjects.

##### **Source of Subjects**

Subjects will be identified from the medical oncology and surgical oncology clinics at RCINJ and by referring providers.

##### **Method to Identify Potential Subjects**

Protocol Number: RCINJ# 051707

PI Name: [name]

Protocol Title: A Phase I Study to Evaluate the Safety of Trigriluzole (FC-4157/BHV-4157) in Combination with PD-1 Blocking Antibodies

52

RESERVED FOR IRB STAMP  
DO NOT MODIFY THIS SPACE

Form Version v120116

**RUTGERS | eIRB**  
**APPROVED**

IRB ID: Pro20170000453  
Approval Date: 10/4/2019  
Expiration Date: 4/3/2020

Patients with advanced unresectable or metastatic cancer will be recruited from the surgical oncology and medical oncology clinics at RCINJ. The treating physician will determine if the patient is a potential candidate for the study and discuss the protocol with the patient.

### **Subject Screening**

The treating physician and study nurse will interview the patient and review the chart to determine if the patient is a potential candidate for the study. Patients who have cancer that is curable by surgery are not eligible to participate, as surgery would be a better choice. Patients whom are considered too frail to participate will not meet eligibility criteria for performance status and organ function and will not be eligible to participate. Subjects who do not meet all inclusion criteria are thought to be unable to tolerate study treatment safety and their enrollment will be recorded as screening failures.

### **Inclusion Criteria**

A patient/subject is eligible for enrollment if *all* of the following inclusion criteria are met.

- 1) Patients must have histologically confirmed solid malignancy or lymphoma that is metastatic or unresectable
- 2) There is reasonable expectation of response to pembrolizumab or nivolumab, and one of the drugs is available from the commercial supply. This includes (but is not limited to) the following tumor types: melanoma, non-small cell lung cancer, renal cell carcinoma, squamous cell carcinoma of the head and neck, bladder cancer, and classic Hodgkin lymphoma.
- 3) The patient must have failed at least one line of standard treatment, with the following exceptions in which a PD-1 antibody is FDA approved in the first-line setting:
  - a. melanoma patients
  - b. non-small cell lung cancer patients without EGFR or ALK genomic tumor aberrations whose tumors have high PD-L1 expression [(Tumor Proportion Score (TPS)  $\geq 50\%$ )] as determined by an FDA-approved test.
- 4) Age  $\geq 18$  years old
- 5) Patients must give informed consent.
- 6) Prior chemotherapy, immunotherapy, radiotherapy or major surgery (including radiation therapy or surgery for treatment of brain metastases) must be

completed at least 3 weeks before study entry. Prior PD-1 or PD-L1 therapy is acceptable.

- 7) Patients must have an ECOG performance status  $\leq 2$  (Appendix A).
- 8) Patients must have normal organ and marrow function as defined below:
  - a. Hemoglobin  $>8.0$  mg/dL (without transfusion in the preceding 7 days)
  - b. Platelets  $\geq 70,000$  / $\mu$ L
  - c. Total bilirubin within normal institutional limits (patients with Gilbert's Syndrome must have a total bilirubin  $< 3.0$  mg/dL).
  - d. AST(SGOT)  $<2X$  institutional ULN
  - e. ALT(SGPT)  $<2X$  institutional ULN
- 9) Patients must have measurable disease, defined as at least one lesion that can be accurately measured in at least one dimension (longest diameter to be recorded) as  $\geq 10$  mm by CT scan, PET/CT scan, MRI or caliper/ruler measurement by clinical exam. Lymph nodes: to be considered pathologically enlarged and measurable, a lymph node must be  $\geq 15$  mm in short axis when assessed by CT scan. Lesions that have been radiated in the advanced setting cannot be included as sites of measurable disease unless clear tumor progression has been documented in these lesions since the end of radiation therapy.
- 10) Ability to swallow pills

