## **1.7.12 TREATMENT EVALUATION/CRITERIA FOR RESPONSE**

### **RECIST and Modified RECIST Definition**

#### **RECIST**

Response and progression will be evaluated in this study using the revised international criteria called RECISTv1.1 proposed by the Response Evaluation Criteria in Solid Tumors (RECIST) Committee. RECIST v1.1 criteria will be **modified** for this protocol to include a stipulation that PD must be confirmed to account for pseudoprogression (tumor flare phenomenon). The first instance of PD must be confirmed by either:

- 1) confirmation of disease progression by repeat assessment 4-12 weeks later OR
- 2) association with clinical deterioration (such as a significant decline in performance status).

Changes in only the largest diameter (unidimensional measurement) of the tumor lesions are used in the RECIST criteria. Note: Lesions are either measurable or non-measurable using the criteria provided below. The term "evaluable" in reference to measurability will not be used because it does not provide additional meaning or accuracy.

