### RECIST Response Categories

#### Evaluation of Target Lesions

Complete Response (CR):	Disappearance of all target lesions
Partial Response (PR):	At least a 30% decrease in the sum of the longest diameter (LD) of target lesions, taking as reference the baseline sum LD.
Progressive Disease (PD):	At least a 20% increase in the sum of the LD of target lesions, taking as reference the smallest sum LD recorded since the treatment started or the appearance of one or more new lesions. In addition to the relative increase of 20%, the sum must also demonstrate an absolute increase of at least 5 mm. (Note: the appearance of one or more new lesions is also considered progression).
Stable Disease (SD):	Neither sufficient shrinkage to qualify for PR nor sufficient increase to qualify for PD, taking as reference the smallest sum LD since the treatment started.

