#### **Secondary Hypotheses and Endpoints**

We hypothesize that combination therapy will lead to regression of tumors. Therefore, the following secondary endpoints will be recorded:

- objective response rate (ORR) according to modified RECIST v.1.1.
- survival time (OS)
- landmark survival rates at 1 and 2 years
- duration of response for responding patients
- time to progressive disease (PFS)

- time to treatment failure
- time to next therapy or death (TTNTD)
- freedom from new metastases

We hypothesize that features in the tumor microenvironment (TME) and/or tumor genome may be associated with response to therapy. Therefore, we will quantify changes in immune cell phenotypes and gene expression, markers of angiogenesis, metabolic effector molecules, and exosomal formation and contents.

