### **Definitions of Evaluable for Toxicity and Response**

**Evaluable for toxicity.** All subjects who received at least one dose of each study drug will be considered evaluable for toxicity.

**Evaluable for objective response.** All subjects who undergo at least one on-study tumor assessment will be considered evaluable for response.

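### Lymphoma is eligible, but response for all subjects is graded only by solid-tumor RECIST and pooled into one ORR, and the nodal rules as written can misgrade node-based disease

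*Combined protocol and SAP*

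**What the plan says.** Eligibility (section 4.1.1, Inclusion Criteria). Criterion 1: "Patients must have histologically confirmed solid malignancy or lymphoma that is metastatic or unresectable". The list of expected tumor types in criterion 2 ends with "bladder cancer, and classic Hodgkin lymphoma". Criterion 9 treats a lymph node as measurable when its short axis on CT is at least 15 mm.

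Response system (section 1.7.12). Response and progression are evaluated "using the revised international criteria called RECISTv1.1 proposed by the Response Evaluation Criteria in Solid Tumors (RECIST) Committee". The one modification is to "include a stipulation that PD must be confirmed to account for pseudoprogression". The section gives no lymphoma criteria. Contrast CT is preferred. PET/CT is allowed where IV contrast is relatively contraindicated, and no metabolic response category is defined.

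Nodal rules (section 1.7.12). Only the largest diameter of a lesion is used. Target CR is "Disappearance of all target lesions", and target PR is a fall of at least 30% in the summed longest diameters. The statement that nodes must be below 10 mm in short axis appears only in the CR row for non-target lesions.

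Endpoint and analysis (section 6.1). The secondary endpoint is "objective response rate (ORR) according to modified RECIST v.1.1". The denominator rule is: "All subjects who undergo at least one on-study tumor assessment will be considered evaluable for response". Categorical outcomes are summarized by counts and percentages with 90% confidence intervals. No split by tumor type is planned.

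**The concern.** The eligibility criteria admit a disease that the response section does not provide for. A lymphoma subject would be graded by a system that is, by its own name, for solid tumors, and would then be counted in the same ORR as everyone else.

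The plan also handles lymph nodes inconsistently. They are measured by short axis at entry, by longest diameter for target response, and by short axis again for non-target CR. I assume that target lesions in lymphoma would be largely nodal, so this inconsistency would matter most there.

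The same assessment feeds the CR count, duration of CR, duration of response and PFS. It also feeds the responder and non-responder grouping in the correlative analyses, and the progression criterion in section 1.7.13.

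**Working it through.** The plan states no ORR figure, target rate or power for ORR, so there is none to reproduce. The total sample size, which bounds the ORR denominator, does reproduce: 9 + 3 = 12 and 21 + 6 = 27, matching the stated 12 to 27.

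**Step 1: nodal rules side by side**

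| Use | Dimension | Rule | Where |
|---|---|---|---|
| Entry | Short axis | At least 15 mm | Inclusion criterion 9 |
| Target CR | None given | Lesion must vanish | Evaluation of Target Lesions |
| Target PR | Longest diameter | Sum falls by at least 30% | Evaluation of Target Lesions |
| Non-target CR | Short axis | Below 10 mm | Evaluation of Non-Target Lesions |

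**Step 2: what the rules do to a target node that returns to normal size**

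(a) All target nodes fall below 10 mm in short axis but stay visible, and the summed longest diameters fall by 30% or more. They have not vanished, so the grade is PR, not CR. Both count as responses, so ORR does not change. The CR count is one lower, and the subject has no duration of CR.

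(b) Take an illustrative subject with a single target node, 20 x 15 mm at baseline and 15 x 9 mm on treatment. The baseline short axis of 15 mm meets criterion 9. The later short axis of 9 mm is normal by the non-target rule. The change in longest diameter is (15 − 20)/20 = −25%, short of 30%, so the grade is SD and ORR is one response lower. This depends on the node's shape: PR needs a longest diameter of at most 0.7 × 20 = 14 mm, so a fall from 20 to 13 mm (−35%) would be PR.

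Neither case is specific to lymphoma. Both apply to any solid tumor with nodal target lesions.

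**Step 3: size in ORR**

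One response scored as SD lowers ORR by 1/N: 1/12 = 8.3 points and 1/27 = 3.7 points. For scale, I take starting counts from the 20–45% single-agent anti-PD-1 response rates quoted in section 1.4.7, rounded to whole subjects. Intervals are exact (Clopper-Pearson) 90%: lower limit Beta(0.05; x, N − x + 1), upper limit Beta(0.95; x + 1, N − x).

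| N | Start | One fewer response |
|---|---|---|
| 12 | 2/12 = 16.7% (3.0–43.8) | 1/12 = 8.3% (0.4–33.9) |
| 12 | 5/12 = 41.7% (18.1–68.5) | 4/12 = 33.3% (12.3–60.9) |
| 27 | 5/27 = 18.5% (7.6–35.1) | 4/27 = 14.8% (5.2–30.8) |
| 27 | 12/27 = 44.4% (28.0–61.8) | 11/27 = 40.7% (24.8–58.3) |

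The documents do not say how many lymphoma subjects to expect. With none enrolled, the lymphoma part of the effect is zero. Subjects without an on-study assessment leave the denominator, so each remaining response would weigh slightly more than shown.

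**The case against.** The strongest reply has four parts.

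First, the CR rule turns a CR into a PR and so cannot change ORR. That stands for case (a). It does not cover case (b), where the grade is SD.

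Second, the nodal defect is general. Melanoma, lung, and head and neck cancers are also eligible and may have nodal target lesions, so moving lymphoma to another system would leave the target-lesion table defective for everyone else. That stands, and the table itself has to be corrected.

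Third, the plan has some safeguards. Section 1.7.12 allows cytology or histology to separate PR from CR. It also has a doubtful residual lesion investigated, by aspirate or biopsy if possible, before CR is confirmed. These provisions can rescue some CRs where tissue is obtained. They do not supply a size rule for target nodes, and they do not touch the SD-versus-PR boundary.

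Fourth, ORR is a descriptive secondary endpoint with no test, it already mixes tumor types, and no lymphoma subject may enroll. All of that stands and limits the weight of the point.

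A reader might infer that lymphoma responses will be misclassified, or that CR and progression are meaningless for these subjects. The documents do not support that. They show that misgrading can happen through the nodal rules, not that it will in every case. They show no mechanism by which progression loses its meaning, and they say nothing about how RECIST performs in lymphoma.

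**Conclusion.** The point holds as a gap in specification, of low severity. Lymphoma is admitted, no lymphoma response criteria are named, and all evaluable subjects enter one ORR. Separately, the nodal rules in section 1.7.12 conflict with one another and with inclusion criterion 9. They can grade a normalized target node as PR instead of CR, or as SD instead of a response.

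Only the second kind of error moves ORR, by 3.7 points per subject at N=27 and 8.3 points at N=12. These shifts are small beside the sampling uncertainty: the 90% interval for 12/27 spans 61.8 − 28.0 = 33.8 points, and for 5/12 it spans 68.5 − 18.1 = 50.4 points. The MTD/RP2D rests on dose-limiting toxicities and is unaffected.

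This sizing assumes that at least one such case occurs. The node in case (b) is illustrative, and the number of lymphoma subjects is unknown and may be zero.

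**What to change.** - In sections 1.7.12 and 6.1, state that the RECIST-based ORR covers solid tumors only. Name prespecified response criteria for lymphoma, and report lymphoma subjects in a separate row.
- In the target-lesion table, apply the short-axis rule to target lymph nodes, so that it agrees with the non-target table and with inclusion criterion 9. This also corrects grading for solid tumors with nodal targets.
- Reconcile the progression criterion in section 1.7.13, which refers to modified RECIST, with whichever system is named for lymphoma.

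The cost is a few sentences and a slightly smaller denominator for the RECIST ORR. If the chosen lymphoma criteria rely on PET/CT, the imaging paragraph in section 1.7.12 must be reconciled as well, because PET/CT is only a fallback there; CT-based criteria would avoid that. The change should be made before any lymphoma response is graded, so that the choice of criteria does not depend on the data.
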